# 6. TOXICITIES AND DOSE DELAYS/DOSE MODIFICATIONS

Subjects enrolled in this study will be evaluated clinically and with standard laboratory tests before and at regular intervals during their participation in this study as specified in Study Calendar & Evaluations.

Subjects will be evaluated for adverse events (all grades), serious adverse events, and adverse events requiring study drug interruption or discontinuation as specified in Study Calendar & Evaluations.

The intent of the study design is for all patients to complete induction, consolidation and maintenance with the exception of those who experience an unacceptable toxicity or if the investigator determines that discontinuation of treatment is in the best interest of the patient. Please see sections 6.2.1 and 6.2.2 below for individual drug exceptions that are applicable throughout the entire study.

#### 6.1 Toxicity

The NCI Common Terminology Criteria for Adverse Events (CTCAE) v5 will be used to grade adverse events. DLTs are defined in detail in section 5.2

#### 6.1.1 Hematologic Toxicity

DLT definition: Grade 3-4 or worse neutropenia or thrombocytopenia occurring after day 56 due to bone marrow hypocellularity and with the bone marrow documented to be free of leukemic infiltration.

#### 6.1.2 Non-hematologic Toxicity

DLT definition: Defined as any grade 3 or worse treatment-related toxicity (excluding grade 4 infections) occurring within the first 56 days.

In general, dose interruptions for grade 3 or 4 non-hematologic toxicities occurring after day 56 will be at the discretion of the primary oncologist. Please see the individual drug sections below for further detail on dose modifications and special exceptions [tables 5,6, 8].

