# 5.1 Dose Escalation Rules

- Three to six subjects will initially be enrolled at dose level 1. If none of the 3 subjects experience a dose limiting toxicity (DLT) during the first cycle of therapy, an additional three subjects will be enrolled at dose level 2. If none of the 3 subjects at dose level 2 experience a dose limiting toxicity (DLT), an additional three subjects will be enrolled at dose level 3. If all subjects in dose level 3 complete the first cycle of therapy without DLT, 3 more subjects will be enrolled into dose level 3 to ensure only 0-1 of 6 subjects have a DLT. There will be no further escalation beyond dose level 3.
- Alternatively, if 1 of the first 3 subjects within any given dose cohort experiences a DLT, an additional 3 subjects will be enrolled at that dose level. If only 1 of the total 6 subjects in a dose level experience a DLT, the study will proceed to the next dose level as planned. If 2 of the total 6 subjects in any given dose cohort experience a DLT, the next lower dose level will be explored and considered the maximum tolerated dose (MTD) if no more than 1 of 6 subjects experience a DLT. If this occurs in cohort 1, the dose will be decreased to cohort -1 and if 2 or more DLTs are reached in dose level -1, the study will be put on hold and a protocol amendment will be considered. [see Section 6.4 for "Stopping Rules"]
- The MTD for Venetoclax in combination with Gemtuzumab Ozogamicin is defined as the dose level at which fewer than 33% of subjects experience a dose limiting toxicity (DLT), and specifically is the dose level at which less than 2 out of 6 subjects experience DLT. That dose will be the recommended Phase II dose (RP2D).
- Once the RP2D has been identified, we will expand this cohort to include an additional six patients to further evaluate the efficacy and safety profile of the RP2D.

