# 5.2 Definition of Dose-limiting Toxicities

Dose-limiting toxicities (DLTs) are defined as an adverse event related (possible, probable or definite) to Venetoclax and/or Gemtuzumab Ozogamicin fulfilling one of the following criteria:

 Hematologic toxicity: treatment-related grade 3 or worse neutropenia and/or thrombocytopenia due to bone marrow hypocellularity present at the end of cycle one (day 28) with an additional 28 days allowed for count recovery (i.e. present at day 56); specifically grade 3 or worse neutropenia or thrombocytopenia with the bone marrow documented to be free of leukemic infiltration. Note: patients who enter the study with grade 3 or worse cytopenias will not be evaluable for hematologic dose-limiting toxicities.

• Non-hematologic toxicity: any grade 3 or worse treatment-related toxicity occurring within the first cycle (excluding grade 3-4 infections during cycle one).

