#### Consider discontinuing Venetoclax if toxicities recur despite two dose duration reductions

# 6.3 **Protocol Therapy Discontinuation**

In addition to discontinuation due to therapy-related toxicities as outlined in section **6.1**, a subject will also be discontinued from protocol therapy and then followed up per protocol under the circumstances outlined below. The reason for discontinuation of protocol therapy will be documented on the electronic case report form (eCRF) and should also be discussed with the study sponsor-investigator.

- Documented disease progression
- Unacceptable toxicity
- The treating physician believes a change of therapy would be in the best interest of the subject
- Follow-up bone marrow biopsy demonstrates either significant residual leukemic blasts or significant cytoreduction with a high percentage residual leukemic blasts, but BM study is deemed by the hematopathologist to demonstrate less than a partial response.
- Bone marrow biopsy during maintenance phase shows stable disease but the treating hematologist believes that the Venetoclax is no longer of benefit.
- DLT as defined above or if there is grade 3 neutropenia or thrombocytopenia after holding Venetoclax for four weeks at the end of cycles 1 or 2
- Patient is unable to comply with protocol requirements
- The subject requests to discontinue protocol therapy, whether due to unacceptable toxicity or for other reasons. If a subject decides to prematurely discontinue protocol therapy ("refuses treatment"), the subject should be asked if he or she may still be contacted for further scheduled study assessments. The outcome of that discussion should be documented in both the medical records and in the eCRF.
- A female subject becomes pregnant
- Development of a second malignancy (except for basal cell carcinoma or squamous cell carcinoma of the skin) that requires treatment which would interfere with this study.
- If protocol therapy is interrupted for  $\geq 30$  days.
- Lost to follow up. If a research subject cannot be located to document survival, the subject may be considered "lost to follow-up." All attempts to contact the subject must be documented.

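### Section 6.1.2 defines a non-hematologic DLT differently from Sections 2.2.1, 5.2 and 12.2.1, so the same patient can count differently in a 3+3 decision

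*Combined protocol and SAP*

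**What the plan says.** Three sections (2.2.1 Primary Endpoint, 5.2 Definition of Dose-limiting Toxicities, 12.2.1 Definition of Primary Endpoint) give the non-hematologic DLT in the same words: "any grade 3 or worse treatment-related toxicity occurring within the first cycle (excluding grade 3-4 infections during cycle one"). Section 5.2 puts the end of cycle 1 at day 28.

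Section 6.1.2, also labelled as the DLT definition, reads: "Defined as any grade 3 or worse treatment-related toxicity (excluding grade 4 infections) occurring within the first 56 days". Its next sentence uses the same cut-off: "dose interruptions for grade 3 or 4 non-hematologic toxicities occurring after day 56 will be at the discretion of the primary oncologist".

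Section 6.1 opens with a pointer, "DLTs are defined in detail in section 5.2", but sets no order of precedence.

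The count feeds the rules in Section 5.1:
- Levels 1 and 2 escalate on 0 of 3: "If none of the 3 subjects experience a dose limiting toxicity (DLT) during the first cycle of therapy". They also escalate on 1 of 3 followed by 1 of 6 in total.
- At level 3, after 0 of 3, "3 more subjects will be enrolled into dose level 3 to ensure only 0-1 of 6 subjects have a DLT".
- A level reached by de-escalation is "considered the maximum tolerated dose (MTD) if no more than 1 of 6 subjects experience a DLT".

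Section 6.3 begins "In addition to discontinuation due to therapy-related toxicities as outlined in section" 6.1. It then lists a DLT as a reason to end protocol therapy, defined only by reference to earlier text.

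**The concern.** The primary endpoint has two definitions in the current text, and they differ on two elements: the observation window (28 or 56 days) and which infections are excluded (grades 3-4 or grade 4 only). Every 3+3 decision, and so the MTD and the recommended phase 2 dose, rests on counting patients with a DLT in groups of 3 or 6. At that size a single patient can decide the outcome.

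The affected events are plausible in this trial. Section 10.2.7 lists infection among the most common reactions to gemtuzumab, and Section 1.2.2 names pneumonia among the most common grade 3/4 events in the cited venetoclax studies. A possible relationship to either drug is enough under Section 5.2. For patients who go straight into consolidation, days 29-56 also contain the second gemtuzumab course, so the two windows cover different drug exposure.

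There is also a patient-level effect. Through Section 6.3 a DLT ends protocol therapy, while Table 8 has a withhold-and-resume rule for non-hematologic toxicity in consolidation. Sites reading different sections could handle the same event differently.

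**Working it through.** **The plan's own figures.** Section 12.3 gives target quantiles of 0.35 and 0.26 and an upper bound of 0.33. The upper bound is (1+1)/(3+3) = 0.333. The value 0.26 is the p at which P(at most 1 of 6) = 0.5, which is 0.264. The value 0.35 matches the midpoint of the p at which P(0 of 3) = 0.5 (0.206) and the p at which P(at most 1 of 3) = 0.5 (0.500), which is 0.353. That reading is inferred, because the formula is not printed. All three depend only on cohort sizes and cut-offs, so they hold under either definition. What changes is who is counted.

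**Step 1. Classify related events under each text.**

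| Event | 5.2 | 6.1.2 |
|---|---|---|
| Grade 3-5 non-infectious, day 14 | DLT | DLT |
| Grade 3 infection, day 14 | no | **DLT** |
| Grade 4 infection, day 14 | no | no |
| Grade 5 infection, day 14 | DLT | DLT |
| Grade 3-5 non-infectious, day 40 | no | **DLT** |
| Grade 3 or 5 infection, day 40 | no | **DLT** |
| Grade 4 infection, day 40 | no | no |

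For non-hematologic events 6.1.2 is strictly broader: every discordant event is a DLT only under 6.1.2.

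**Step 2. Find where one reclassified patient matters.**
- 0/3 becomes 1/3 at level 1 or 2: escalation becomes expansion to six.
- 1/6 becomes 2/6 at any level: acceptable becomes exceeded.
- No change of decision if the patient already has a DLT, if 0/6 becomes 1/6, or if 0/3 becomes 1/3 at level 3, where three more are enrolled either way.

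**Step 3. Illustrate the size.** All rates here are assumed. With p the probability that a patient has a DLT, and two or more DLTs in the first three taken as not clearing:
- Levels 1-2: P(clear) = (1-p)³ + 3p(1-p)⁵
- At most 1 of 6 (level 3, or a de-escalated level with its six patients taken on their own): P(clear) = (1-p)⁶ + 6p(1-p)⁵

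At p = 0.20 the first is 0.512 + 0.6 × 0.32768 = 0.709. The second is 0.262 + 1.2 × 0.32768 = 0.655.

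Let 6.1.2 add 5, 10 or 20 percentage points to p:

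| p under 5.2 | Rule | Under 5.2 | +5 | +10 | +20 |
|---|---|---|---|---|---|
| 0.20 | Levels 1-2 | 0.709 | 0.600 | 0.494 | 0.309 |
| 0.20 | At most 1 of 6 | 0.655 | 0.534 | 0.420 | 0.233 |
| 0.10 | Levels 1-2 | 0.906 | 0.814 | 0.709 | 0.494 |
| 0.10 | At most 1 of 6 | 0.886 | 0.776 | 0.655 | 0.420 |

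The non-hematologic DLTs under 5.2 are a subset of those under 6.1.2. If hematologic DLTs are counted alike, each drop is therefore the probability that the same patients give a different result for that level. At base 0.20 the drops are 0.109, 0.214 and 0.399 (levels 1-2) and 0.121, 0.235 and 0.422 (at most 1 of 6).

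If the extra 5, 10 or 20% is instead a share of patients without a 5.2 DLT, then p = 0.20 + 0.80e = 0.24, 0.28 or 0.36. The drops become 0.087, 0.173 and 0.330 (levels 1-2) and 0.098, 0.191 and 0.355 (at most 1 of 6).

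**The case against.** The best counter-argument is that the documents largely show which text governs. Section 6.1 sends the reader to 5.2, three sections match word for word, and 5.1 also speaks of the first cycle. On that view 6.1.2 is a stray restatement in a dose-modification section. Part of this stands: 5.2 is the likelier operative text. But the pointer gives it no priority over a different rule restated beneath it, and 6.3 makes a DLT a reason to end therapy without saying which definition applies.

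Some supporting signs are weaker than they look. The second use of day 56 in 6.1.2 concerns dose interruption, and the day-56 limit in 6.4 fits the hematologic recovery window already in 5.2. The conflict does not need either.

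The objections on size also have force. No rate comes from the documents, and an extra 20 points is only the top of an assumed range. Treatment failures leave the study after induction, so fewer patients may be observed through days 29-56, although adverse events are still recorded for 30 days after treatment or until new therapy. That limit does not touch grade 3 infections in cycle 1. Moving from 0/3 to 1/3 does not itself change the MTD: three patients are added, and escalation follows if none of them has a DLT. Only 1/6 to 2/6 changes it directly.

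Finally, the subset argument covers non-hematologic events only. Section 6.1.1 places the hematologic DLT after day 56, whereas 5.2 requires it to be present at day 56, so Section 6.1 read as a whole need not be broader than 5.2.

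**Conclusion.** The concern holds. The current text contains two incompatible definitions of the non-hematologic DLT, the main component of the only primary endpoint that is assessable in every treated patient, and they differ on both window and infection exclusion. That finding is textual and needs no assumption. It must be fixed because one patient can move a level from acceptable to exceeded.

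The size is unknown and could be small, since only events judged related count. Under the assumed rates (10% or 20% under 5.2, a further 5 to 20 percentage points under 6.1.2, hematologic DLTs counted alike), the chance that a level clears falls by roughly 0.09 to 0.47. The largest fall is 0.886 - 0.420 = 0.466.

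Two lesser points may be loose wording: 5.1 ties DLTs to the first cycle although the hematologic DLT in 5.2 runs to day 56, and 6.1.1 and 5.2 differ on its timing.

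**What to change.** Adopt one DLT definition covering the non-hematologic window, the infection exclusion and the hematologic timing. Its clinical content is for the sponsor to choose. State it in Section 5.2 and repeat it verbatim in 2.2.1 and 12.2.1. Replace the definition lines in 6.1.1 and 6.1.2 with a cross-reference to 5.2, and make 5.1, 6.3 and 6.4 refer to that definition and its window. Reconcile the DLT discontinuation rule in 6.3 with Table 8 for events in consolidation.

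The cost is a wording amendment and a re-read of any events already classified, with no extra patients or procedures. If cohorts have been decided, the re-read could reopen one of those decisions.

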# 6.2 Dose delays/modifications

During induction and consolidation, there will be no dose reductions of study drugs for hematologic toxicity. For patients in CRi after day 28 of induction, Venetoclax may be held for up to four weeks, to allow for platelet or ANC recovery. *Note CBC will be performed at least twice weekly and consolidation should start as soon as platelets recover to* 100 x 10^9/L *and ANC recovers to* 1.0 x 10^9/L. If platelets or ANC do not recover within 4 weeks, patients will not receive further GO and will enter the Venetoclax maintenance phase. Patients who enter the maintenance phase must have platelets  $\geq 50 \times 10^{9}$ /L and an ANC  $\geq 1.0 \times 10^{9}$ /L. If there is a grade 3 or worse cytopenia present after holding Venetoclax for up to 4 weeks, patients will be removed from study.

At the end of consolidation, Venetoclax may be held again for up to four weeks, maintenance phase can be started as soon thrombocytopenia or neutropenia improves to less than a grade 3 toxicity, unless there is still residual disease in the bone marrow, in which case treatment can proceed regardless of ANC/platelet count. NOTE: If a grade 3 cytopenia persists after 4 weeks of holding Venetoclax for up to 4 weeks following induction or consolidation, patients will be removed from study.

# 6.2.1 Gemtuzumab

# Table 5. Gemtuzumab Delay/Discontinuation

Event	Gemtuzumab Action
Persistent Thrombocytopenia	Discontinue if platelets do not recover to $\ge 100 \times 10^9/L$ after temporary cessation of Venetoclax for four weeks
Persistent neutropenia	Discontinue if ANC does not recover to $\ge 1.0 \times 10^9$ /L after temporary cessation of Venetoclax for four weeks
VOD	Discontinue
Total bilirubin $> 2 \times ULN$ , or AST and/or ALT $> 2.5 \times ULN$	Interrupt until recovery of total bilirubin to ≤2 times ULN and AST and/or ALT to ≤2.5 times ULN.

The scheduled dose will be omitted if there is a delay of 3-6 days between sequential infusions.

Table 6. Gemtuzumab Schedule for Interruptions

Time from missed dose	Action
<3 days	Give missed dose
3-6 days	Skip dose
≥7 days	Off study

# 6.2.2 Venetoclax

Venetoclax toxicity event	Current (cohort) dosing regimen	Modification of dosing regimen
1 st event	28 days	28 days
2 nd event	28 days	21 days
3 rd event	21 days	14 days
4 th event	14 days	discontinue

# Table 7. Dose Duration Reduction for Venetoclax Toxicity (Maintenance)

There will be no dose reductions of Venetoclax for hematologic toxicity during cycles 1 and 2. Patients who are in CRi after either cycle may temporarily discontinue Venetoclax for up to four weeks to allow for platelet or ANC recovery. Patients who enter the maintenance phase must have platelets  $\geq 50 \times 10^9/L$  and an ANC  $\geq 1.0 \times 10^9/L$ 

If a dose reduction is required, please follow the guidelines in Table 7. Missed Venetoclax doses are not to be made up.

Toxicity	Occurrence	Action					
Tumor Lysis Syndrome (TLS)							
TLS defined by the Cairo-Bishop criteria; see Appendix IV	Any	Implement standard TLS treatment (increase IVF). Withhold Venetoclax if TLS labs do not improve by 25% within 24 hours. Resume once TLS labs improve.					
Non-Hema	atologic Toxicities	s (Consolidation and Maintenance only)					
toxicities 2 nd and		Withhold Venetoclax. Once the toxicity has resolved to Grade 1 or baseline, resume at same dose.					
		Withhold Venetoclax. Once the toxicity has resolved to Grade 1 or baseline, resume at a reduced dosing duration (see Table 7).					
	Hematologic To	oxicities (Maintenance only)					
Grade 4 neutropenia with or without fever; or Grade 4 thrombocytopenia	1 st occurrence	Interrupt Venetoclax. To reduce infection risks associated with neutropenia, G-CSF may be administered if clinically indicated, provided there is bone marrow confirmation of leukemia clearance. Once the toxicity has resolved to Grade 2 or baseline, resume at the same dose duration (Table 7).					
	2 nd occurrence	Interrupt Venetoclax. Consider using G-CSF as clinically indicated. Once the toxicity has resolved to Grade 2 or baseline, follow dose duration reduction guidelines (Table 7).					

# Table 8. Venetoclax Dosing Regimen Modifications

3rd and subsequent occurrencesInterrupt Venetoclax. Consider using G-CSF as clinically indicated. If toxicity remains at grade 3, may discuss with PI regarding treatment options. If grade 4 toxicity persists, remove from study (Table 7).
--

#### Consider discontinuing Venetoclax if toxicities recur despite two dose duration reductions

# 6.3 **Protocol Therapy Discontinuation**

In addition to discontinuation due to therapy-related toxicities as outlined in section **6.1**, a subject will also be discontinued from protocol therapy and then followed up per protocol under the circumstances outlined below. The reason for discontinuation of protocol therapy will be documented on the electronic case report form (eCRF) and should also be discussed with the study sponsor-investigator.

- Documented disease progression
- Unacceptable toxicity
- The treating physician believes a change of therapy would be in the best interest of the subject
- Follow-up bone marrow biopsy demonstrates either significant residual leukemic blasts or significant cytoreduction with a high percentage residual leukemic blasts, but BM study is deemed by the hematopathologist to demonstrate less than a partial response.
- Bone marrow biopsy during maintenance phase shows stable disease but the treating hematologist believes that the Venetoclax is no longer of benefit.
- DLT as defined above or if there is grade 3 neutropenia or thrombocytopenia after holding Venetoclax for four weeks at the end of cycles 1 or 2
- Patient is unable to comply with protocol requirements
- The subject requests to discontinue protocol therapy, whether due to unacceptable toxicity or for other reasons. If a subject decides to prematurely discontinue protocol therapy ("refuses treatment"), the subject should be asked if he or she may still be contacted for further scheduled study assessments. The outcome of that discussion should be documented in both the medical records and in the eCRF.
- A female subject becomes pregnant
- Development of a second malignancy (except for basal cell carcinoma or squamous cell carcinoma of the skin) that requires treatment which would interfere with this study.
- If protocol therapy is interrupted for  $\geq 30$  days.
- Lost to follow up. If a research subject cannot be located to document survival, the subject may be considered "lost to follow-up." All attempts to contact the subject must be documented.

If a subject decides to withdraw from the study (and not just from protocol therapy) all efforts should be made to complete the final study assessments. The site study team should contact the subject by telephone or through a clinic visit to determine the reason for the study withdrawal. If the reason for withdrawal is an adverse event, it will be recorded on the eCRF.

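### Section 6.3 ends protocol therapy for any DLT, yet the Table 8 tumor lysis row, and to a lesser extent the Table 5 hepatic row, lets treatment continue after the same cycle 1 event

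*Combined protocol and SAP*

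**What the plan says.** The stopping rule is in section 6.3. It opens with "a subject will also be discontinued from protocol therapy and then followed up per protocol under the circumstances outlined below", and its list includes "DLT as defined above or if there is grade 3 neutropenia or thrombocytopenia after holding Venetoclax for four weeks" at the end of cycle 1 or 2. It makes no exception for a DLT that reverses.

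Section 5.2 defines the non-hematologic DLT as "any grade 3 or worse treatment-related toxicity occurring within the first cycle", with grade 3-4 infections in that cycle as the only exclusion. Sections 2.2.1 and 12.2.1 repeat this. A note after the definition also removes events clearly due to progression, intercurrent illness or other drugs.

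The continuation rules are in section 6.2. The TLS row of Table 8 applies at any occurrence. After standard TLS treatment it says: "Withhold Venetoclax if TLS labs do not improve by 25% within 24 hours. Resume once TLS labs improve". For GO, the hepatic row of Table 5 says: "Interrupt until recovery of total bilirubin to ≤2 times ULN and AST and/or ALT to ≤2.5 times ULN". Table 6 then decides what happens to the delayed GO dose. The introduction to section 6 describes sections 6.2.1 and 6.2.2 as containing "individual drug exceptions that are applicable throughout the entire study".

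**The concern.** A site with a drug-related grade 3 or worse TLS event during ramp-up or cycle 1 finds two instructions: section 6.3 ends both drugs, and Table 8 restarts venetoclax. The protocol plans for this toxicity. It uses a ramp-up because of TLS risk (section 5.4), warns that the risk remains despite it (section 5.7), and schedules chemistry at least every 8 hours in ramp-up (study calendar, footnote 8). Raised AST and ALT are likewise listed among the common GO reactions (section 10.2.7).

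If sites resolve the conflict differently, patients with the same event at the same dose level differ in further exposure, in whether they reach consolidation, and in the recorded reason for stopping. A patient's safety would also depend on which section the site happened to read.

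**Working it through.** The plan gives no figure to reproduce. The check is whether the events that trigger the section 6.3 stop overlap with those the tables allow to continue, and whether any text sets precedence.

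**1. Events that stop therapy.** Related, non-hematologic, grade 3 or worse, in cycle 1, not an infection. Ramp-up days -2 to 0 belong to cycle 1 (Table 2, study calendar). Section 6.1.2 has a second definition, "Defined as any grade 3 or worse treatment-related toxicity (excluding grade 4 infections) occurring within the first 56 days". Its window and infection exclusion differ, but it too exempts neither TLS nor liver events, so the result holds under either definition.

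**2. Side by side.**

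| Feature | TLS, Table 8 | Hepatic, Table 5 with Table 6 |
|---|---|---|
| Trigger | Cairo-Bishop TLS, any occurrence | Bilirubin above 2 x ULN, or AST/ALT above 2.5 x ULN; no ceiling |
| Phase limit | None; the rows below it are confined to later phases | None |
| Drug affected | Venetoclax | GO only |
| After improvement | Restart stated outright | Restart implied. Table 6: under 3 days late, give; 3-6 days, skip; 7 days or more, off study |
| Section 6.3 at grade 3 or worse | Ends all protocol therapy | Ends all protocol therapy |

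**3. Overlap for TLS.** With no grade or phase limit, the row includes every related grade 3 or worse TLS event in ramp-up or cycle 1. Section 11.1.1 treats a laboratory change as an adverse event only if it causes signs or symptoms or needs treatment or further tests. TLS handled under Table 8 is treated, so it qualifies.

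**4. Overlap for hepatic events.** A lower trigger without a ceiling also takes in grade 3 or worse events. The overlap shrinks in three ways. Events below grade 3 are not DLTs. Section 11.1.1 removes some isolated laboratory changes. Once a GO dose is 7 or more days late, Table 6 takes the patient off study, so both routes end treatment. What remains is the related grade 3 or worse event with a GO hold shorter than 7 days.

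**5. Precedence.** The introduction to section 6 extends the drug rules to the whole study. Section 6.1.2 refers to Tables 5, 6 and 8 as exceptions. Neither mentions the DLT item in section 6.3, and section 6.3 does not mention the tables.

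**6. Exposure at stake.** Planned GO infusions: 3 (cycle 1) + 2 (cycle 2) = 5.
- TLS in ramp-up: 0 of 5 under section 6.3; up to 5 of 5, with venetoclax, if treatment goes on.
- Hepatic DLT after the first infusion: 1 of 5 under section 6.3; up to 5 of 5 under Tables 5 and 6 if the delay is under 3 days, at most 4 of 5 if a dose is skipped.

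**7. DLT count.** Section 5.2 counts occurrence, so a patient normally counts once whichever rule follows. One case is less clear. Section 12.4 calls a patient evaluable for toxicity only after at least one dose of each drug. A ramp-up TLS DLT stopped under section 6.3 precedes any GO. If section 12.4 is meant to define the DLT-evaluable set, which the plan does not say, that patient would drop out, but would stay in if treatment resumed.

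**8. Weight of one patient.** 1/6 = 17% of a six-patient cohort. With the expansion, 6 + 6 = 12 at the recommended dose, and 1/12 = 8.3%.

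**The case against.** The best answer is that the passages can be read in order: Tables 5 and 8 cover events below the DLT threshold, and section 6.3 takes over once section 5.2 is met. Table 8 gives this some support, since its general non-hematologic rows are confined to consolidation and maintenance and so leave cycle 1 to the DLT rule. The opposite order can also be argued, because section 6.1.2 calls the tables exceptions. Section 6.3 further asks that the reason for discontinuation be discussed with the sponsor-investigator, which limits divergence between sites.

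Both orders are workable, but neither is written down, and they give opposite results. The phase limit on the neighbouring rows also makes its absence from the TLS row more noticeable.

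Other parts of the objection stand and set the limits of the point. A reader might infer:

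- That Table 5 tells sites to resume just as Table 8 does. It does not: it covers GO alone, says only to interrupt until recovery, and is bounded by Table 6.
- That accepting 1 DLT in 6 at the recommended dose makes such a patient likely. That allowance covers every DLT type, including persistent cytopenia, where this conflict does not arise. CTCAE v5 cut-offs are not reproduced, and Appendix IV defines laboratory TLS without grades.
- That 8.3 percentage points is the error in the response rate. It is one patient's weight, and would be an error only if the choice of rule alone changed that patient's response.
- That dose escalation is compromised, or a comparison between sites spoiled. The DLT count is generally the same either way, and no between-site comparison is planned.

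It may also be said that nothing links DLT classification to resumption. That is true of section 5.2. Section 6.4, however, lets escalation proceed once all patients in a cohort have recovered from DLTs before day 56, which leaves room to think that recovery undoes the count.

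**Conclusion.** The contradiction is real and should be corrected. It is clear for related grade 3 or worse TLS in ramp-up or cycle 1. It is partial for related grade 3 or worse hepatic events, limited to GO holds shorter than 7 days counted from the missed dose. The effect falls on patient safety, exposure, receipt of consolidation, the recorded reason for discontinuation and the descriptive response and survival results. The primary endpoint is generally untouched, with the section 12.4 reading for ramp-up events as the possible exception. How often the conflict will arise cannot be estimated from the documents.

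This rests on two assumptions: that section 6.3's reference to a DLT defined above means section 5.2 or section 6.1.2, both of which include these events; and that the TLS row is meant to apply in cycle 1, as its lack of a phase limit and the introduction to section 6 indicate. Which clinical rule is right is not a matter for this review.

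**What to change.** Reconcile the DLT item in section 6.3 with the TLS row of Table 8 and the hepatic rule in Tables 5 and 6. Two forms would do, and the sponsor decides between them:

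- state in the tables that these rows do not apply once an event meets section 5.2; or
- state in section 6.3 which DLT types follow the tables instead of discontinuation.

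Cross-refer in both directions, and make the remark about exceptions in section 6.1.2 agree. Add to section 5.2 or 6.4 that the event counts as a DLT for escalation whether or not treatment resumes or the event recovers. That sentence should also cover a DLT that occurs in ramp-up, before the first GO dose.

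The cost is one wording amendment and a memo to sites. No extra patients or data are needed.
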